12.3 Planned Interim Analyses (if applicable)

There are no planned interim analyses for the primary or secondary outcomes. We will provide summary statistics of social health determinants (insurance, transportation, social relationship resources) and health behavior (tobacco and alcohol use) to each Tribal community based upon the baseline assessment only. This will be returned after we complete our last enrollee (expected in month 14 of recruitment).

12.4 Final Analysis Plan

Descriptive analyses will include calculating means and proportions and their associated measures of variability. We will also compare key sociodemographic differences across those who do and do not complete the study (attrition analysis). As per CONSORT guidelines¹⁷ we will not statistically compare participant baseline characteristics across treatment arms.

Missing data. We will multiply impute missing values for the primary outcome for all participants enrolled and randomly assigned to a treatment (intention to treat). We will impute within each treatment group¹⁸ based upon key sociodemographic factors (maternal age and education; tribe; child sex) assuming the data are missing at random. Multiply imputed estimates of regression coefficients and standard errors will be combined using Rubin's rules. The primary outcome is a continuous variable.

The focal intention to treat analysis of the intervention will be evaluated by regressing dmfs at follow up on a binary treatment group variable using robust variance estimates. We will include child sex, child age in months at follow up and site (Hopi/Crow) as covariates. Although randomization should balance the treatment groups, age and sex are strongly associated with dmfs scores⁷ and covarying those variables should increase efficiency. Covarying child age also statistically controls for follow up length. In contrast, covarying the (log) number of tooth surfaces in analysis of childhood caries did not predict dmfs in a similar RCT.² We are not powered to compare treatment differences across site but using site as a covariate will increase sensitivity in the context of possible site differences in caries.

Robust variance estimation in OLS regression will provide more accurate variance estimates in the presence of assumptive violation, i.e., heteroscedasticity. If the model is homoscedastic robust regression will provide estimates close to non-robust OLS estimates.¹⁹ This approach obviates the need to prespecify the correct form of assumptive violation.

Analysis of the oral health secondary outcome (dmft) will parallel dmfs analyses. Other secondary outcomes involving questionnaires will regress post-test scores (Visit 6) on a binary treatment indicator variable using baseline values as a covariate.

Should we observe treatment effects on caries we will conduct exploratory analysis of possible mediators including oral health knowledge, behavior, efficacy, and structural barriers such as transportation.

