The healthy lifestyle intervention will provide education and support for mothers regarding pregnancy, postpartum challenges, food preparation for children 12 months and older, infant nutrition, and parenting. This also includes a short module on oral health. The intervention will be administered by trained CHRs. Six sessions are scheduled for the healthy lifestyle group, with timing parallel to the timing of sessions in the oral health arm. Children in this arm will receive a fluoride varnish application by study staff at 12 months and 24 months. Children in the HL arm in the early cohort will receive a third FV application after their final study visit at child age 30-36 months.

Children in both groups will be scheduled for a full oral health assessment at 12 (Visit 4) and 24-27 months (Visit 6). Earlier recruits (through month 8 recruitment) will be followed up longer for a final oral assessment (Visit 7 at 30-36 months of age).

Assessments will be conducted by calibrated dentists and/or hygienists, masked to the study condition. Mothers will be reminded of their appointments through follow-up phone calls and/or in person visits from the Community Health Representatives. Dentists will provide oral assessment data to study staff who will securely upload the data into REDCap and securely store the records.

Secondary outcomes of oral health knowledge, behaviors, and attitudes and knowledge of maternal and child health issues not related to oral health will be assessed using questionnaires. Oral health knowledge and maternal child health knowledge will be assessed at Visits 1, 4, 5 and 6. Oral health attitudes will be assessed at Visits 1, 4 and 6 and oral health behavior will be assessed at Visits 4, 5 and 6. Survey data will be securely collected via laptop or tablet using REDCap software.

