12 STATISTICAL CONSIDERATIONS

12.1 Study Hypotheses

This study examines the effect of a bundled “best practices” intervention that includes locally tailored dietary and oral health education provided during pregnancy and the postnatal period; 2) oral health care of children including the application of fluoride varnish; 3) motivational interviewing with children’s mothers; and 4) patient navigation of existing oral health and other social services in each study community, facilitated by CHRs. This treatment will be compared to a healthy lifestyle intervention which includes maternal and child health, child developmental milestones, nutrition and other healthy behavior.

Primary outcome

Number of decayed, missing or filled primary tooth surfaces – dmfs – at the last oral assessment

The hypothesis for the primary outcome dmfs is that a bundled “best practices” oral health and fluoride varnish intervention will reduce early childhood caries relative to a healthy lifestyle intervention comparison group.

Ho: mean oral health group dmfs = mean healthy lifestyle group dmfs

Ha: mean oral health group dmfs \neq mean healthy lifestyle group dmfs

If this hypothesis is confirmed we will then calculate the prevented fraction which “...is the difference in mean caries increments between the treatment and control groups expressed as a percentage of the mean increment in the control group” (Marinho et al. 2013, p. 1). This will be a descriptive supplement to the primary endpoint analysis rather than a separate statistical hypothesis test. We do not plan to analyze twelve month dmfs data but will incorporate 12 month assessments in models to multiply impute missing dmfs scores for the last assessment.

Secondary endpoints

Average number of decayed, missing or filled teeth at the last oral assessment (dmft; excluding non-cavitated lesions)

Hypothesis: average dmft will be lower in the oral health group

Ho: oral health group average dmft = healthy lifestyle group average dmft

Ha: oral health group average dmft \neq healthy lifestyle group average dmft

Mother/caregiver oral health knowledge at Visit 6

Hypothesis: caregiver oral health knowledge will be higher in the oral health group

Ho: mean oral health group oral health knowledge = mean healthy lifestyle group oral health knowledge

Ha: mean oral health group oral health knowledge \neq mean healthy lifestyle group oral health knowledge

Mother/caregiver oral health behavior at Visit 6

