12.2 Sample Size Considerations

A Cochrane meta-analytic review⁹ estimated that fluoride varnish reduces the prevalence of decayed, missing and filled first teeth surfaces (dmfs) by 37%. An Indian Health Services survey reported a mean dmfs in 2-year olds of 10.05 (standard deviation [SD]=16.27).¹⁴ A 37% reduction from this low base rate would require prohibitively large samples from these communities. To increase sensitivity and efficiency we will follow our sample from a minimum of 2 years and some children to a maximum of 3 years of age. Recent data from 3-year olds on the Navajo Nation showed a mean dmfs of 18.2 (SD=19.4). Therefore, for sample size calculations, we estimate values halfway between ages 2 and 3, i.e., mean dmfs=14 (SD=17.25). Using Stata 15.1 (StataCorp, College Station, TX) with power = 0.80, alpha = 0.05 (two tailed) for an independent *t*-test a sample of 352 is necessary to detect a 37% reduction in caries experience (dmfs of 14 vs 8.8; SD=17.25). To cover the estimated 19% attrition rate reported in the Cochrane review would require 434 participants. This is the theoretical maximum sample size necessary in this context. However, sample size estimates are highly sensitive to the estimated variability of dmfs measurements. A 35% reduction in the standard deviation (SD=11.2) for the same effect size would require only 150 participants for power = 0.80 (N=185 to cover attrition). Prior studies in AI groups have not evaluated fluoride varnish application in combination with prenatal maternal intervention using MI techniques and care coordination. This novel and intensive treatment combination should produce a larger effect than varnish alone and also reduce extreme caries experience, i.e., reduce dmfs variability. Our statistical sensitivity is also enhanced by following early enrollees up to an average expected age of ~ 2.5 years. Our recruitment timeline targets enrollment of 350 pregnant women across both sites. With 19% attrition we would retain an effective sample size of 283.5. To be

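### The questionnaire outcomes have no missing-data method and ignore interim scores already scheduled, so the Visit 6 contrast is open to bias if dropout differs by arm

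*Combined protocol and SAP*

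**What the plan says.** Section 12.4 sets a missing-data method for dmfs: "We will multiply impute missing values for the primary outcome for all participants enrolled and randomly assigned to a treatment (intention to treat"). Section 12.1 adds that the investigators "will incorporate 12 month assessments in models to multiply impute missing dmfs scores for the last assessment". For the second caries outcome, "Analysis of the oral health secondary outcome (dmft) will parallel dmfs analyses", so it is reasonable to read dmft as covered too.

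The other four secondary outcomes (oral health knowledge, behavior, attitudes, and maternal/child health knowledge) have one sentence: "Other secondary outcomes involving questionnaires will regress post-test scores (Visit 6) on a binary treatment indicator variable using baseline values as a covariate". No imputation, repeated-measures model, missing-data assumption or sensitivity analysis is given for them.

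Section 4 schedules the same instruments earlier: "Oral health knowledge and maternal child health knowledge will be assessed at Visits 1, 4, 5 and 6", and "Oral health attitudes will be assessed at Visits 1, 4 and 6 and oral health behavior will be assessed at Visits 4, 5 and 6". Attitudes therefore have no Visit 5 score, and behavior has no Visit 1 score.

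Section 5.5.2 says that data from mothers who withdraw will be included up to the point of withdrawal. It also asks for an early-termination questionnaire on knowledge, attitudes and behavior. Section 12.4 assigns neither a role in the questionnaire analyses.

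**The concern.** A regression of the Visit 6 score on treatment and baseline drops every mother without a Visit 6 score. A mother seen at Visits 4 and 5 and then lost contributes nothing, although her last scores are probably the best available predictors of the missing one. The plan accepts this principle for dmfs, where the 12-month assessment enters the imputation model, but does not carry it over to the questionnaires. Nor can a Visit 6-only regression honor the Section 5.5.2 statement about data up to withdrawal.

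Four of the five secondary outcomes are affected. If low scorers leave one arm more than the other, the estimated effect on knowledge, behavior or attitudes moves for a reason unrelated to treatment. The arms receive different curricula from different, unmasked community health representatives, so such dropout is plausible, though the documents do not show it. The primary caries comparison is not affected.

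**Working it through.** **Inputs from the documents.** Section 12.2: "Our recruitment timeline targets enrollment of 350 pregnant women across both sites"; "With 19% attrition we would retain an effective sample size of 283.5", rounded down to 282 (141 per group); power 0.81 for knowledge at 65% versus 80% correct.

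**Reproducing the plan's figure.** Two proportions, two-sided alpha 0.05, n = 141 per group, mean proportion 0.725:
- null SE = √(2 × 0.725 × 0.275 / 141) = 0.0532
- alternative SE = √((0.65 × 0.35 + 0.80 × 0.20) / 141) = 0.0524
- power = Φ((0.15 − 1.96 × 0.0532) / 0.0524) = Φ(0.873) = 0.809, matching 0.81

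Knowledge is thus powered on expected completers, which fits an analysis of observed mothers only. The expected loss is 350 × 0.19 = 66.5, or 350 − 282 = 68 after rounding.

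**Assumptions not in the documents.** Score SD 15 points (range 10 to 20). Between-visit correlations either equal (0.3 to 0.7) or declining with time (0.40 to 0.62). Nineteen percent missing at Visit 6 in each arm. Where dropout depends on score, the log-odds of dropout rise by 1 for each SD that the Visit 5 score is lower.

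**Formula.** Under this rule the mothers who remain average m = 0.165 SD above the full arm at Visit 5. The shift in that arm's Visit 6 mean is approximately
- with no baseline covariate: SD × ρ56 × m
- baseline-adjusted: SD × (ρ56 − ρ15ρ16) × m

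The subscripts are visit numbers. Bias in the contrast is the shift in the Oral Health arm minus the shift in the Healthy Lifestyle arm, so equal shifts cancel.

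**Example.** Equal correlation 0.5, low scorers leaving the Oral Health arm only:
- adjusted: 15 × (0.5 − 0.25) × 0.165 = 0.62
- unadjusted: 15 × 0.5 × 0.165 = 1.24

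Opposite-direction dropout doubles both. Large simulations agree:

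| Dropout pattern | Adjusted, equal correlations 0.3–0.7 | Adjusted, declining 0.40–0.62 | No baseline (behavior), equal 0.3–0.7 |
|---|---|---|---|
| Alike in both arms, equal rates | about 0 | about 0 | about 0 |
| Low scorers leave Oral Health arm only | +0.5 to +0.6 | +1.1 to +1.2 | +0.75 to +1.75 |
| Opposite directions by arm | +1.1 to +1.3 | +2.2 | +1.4 to +3.5 |

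Further results:
- With one common dropout rule and a true 15-point effect, the arms lose about 13% and 25%, and the adjusted bias is −0.3 to −0.4.
- With dropout depending on baseline only, bias is about 0.
- In the one-arm and opposite-direction cases bias scales with SD. For opposite directions at equal correlation 0.5 it is 0.9 to 1.7 points as SD runs from 10 to 20.
- Using the interim scores (Visit 4 alone when dropout depends on Visit 4, as attitudes would require) brings bias to about zero.
- If half of the dropouts have no Visit 4 or 5 score, +0.3 to +0.6 points remain at equal correlation 0.5.

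**Scale.** At correlation 0.5 the adjusted SE is 15 × √(1 − 0.5²) × √(2/141) = 1.55. Without a baseline it is 15 × √(2/141) = 1.79. At SD 15 the difference detectable with 80% power in an unadjusted test is about 2.80 × 1.79 = 5.0 points.

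**The case against.** Baseline-adjusted regression at a prespecified visit is a standard analysis, and the outcomes are secondary. The plan also limits loss: mothers who stop the intervention are asked to stay in follow-up, an early-termination questionnaire is requested, and an attrition analysis is planned. The 19% comes from a published review and is used for the final dental assessment, which is Visit 7 for the early cohort, so loss at the Visit 6 survey could be smaller. All of this stands, and it limits the size of the problem. It does not supply a missing-data method or a use for the interim scores.

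Four stronger readings are tempting, and the documents do not support them:
- **Score-related dropout by itself biases the results.** It does not if it acts alike in both arms at equal rates. Nothing in the documents shows that dropout will differ by arm.
- **The trial holds the data to correct the bias in full.** The first post-baseline survey is at child age 12 months, and mothers lost before it have no post-baseline score. The timing of dropout is not given.
- **The plan chooses an observed-only analysis.** It never says so; this is inferred from its silence and from the power calculation on 282.
- **The questionnaire analyses abandon intention to treat.** Mothers are still compared as randomized. What is missing is an account of those without a Visit 6 score.

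**Conclusion.** The point holds conditionally. The questionnaire outcomes have no stated missing-data method, and no planned efficacy analysis uses their Visit 4 and 5 scores. Under the assumed inputs, bias in the baseline-adjusted outcomes runs from 0 to about 1.2 points with one-arm dropout and up to about 2.2 with opposite-direction dropout. For behavior it reaches about 3.5.

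Against the stated 15-point difference these are 8% (1.2/15), 15% (2.2/15) and 23% (3.5/15). Against the SE, one-arm bias in the adjusted outcomes stays below one SE. The opposite-direction cases can exceed it, and for behavior can approach two (3.5/1.79 = 1.96). A true 15-point effect would survive; a result near the 5-point detectable difference might not.

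Every magnitude rests on an SD, correlations and a dropout rule that the documents do not give, so these are ranges and not a forecast. The change is worth making before analysis because it costs little. It is not a threat to the trial's primary conclusion.

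**What to change.** In Section 12.4, analyse each questionnaire outcome in all randomized mothers in one of two ways:
- a likelihood-based repeated-measures model with Visits 4, 5 and 6 as responses (4 and 6 for attitudes), treatment-by-visit, baseline-by-visit where a baseline exists, site, unstructured covariance, and the Visit 6 contrast as the test; or
- the existing within-arm multiple imputation extended to these outcomes, with Visit 4, Visit 5 and early-termination scores as predictors.

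Keep the single-visit regression as a sensitivity analysis and add one that allows for data missing not at random. State that mothers lost before Visit 4 are only partly recoverable. State what replaces the baseline covariate for behavior, which is not measured at Visit 1. Reconcile the Visit 5 procedure list in Section 7.3.5, which omits the knowledge and behavior surveys, with Sections 3.2 and 4, which place them at that visit.

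The cost is plan wording and modest programming, with no new data. Precision is close to unchanged and in some scenarios slightly worse: with about 20% missing and score-related dropout in both arms, one simulation gave an SE of 1.70 against 1.66; with random dropout it gave 1.56 against 1.59.

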A very detailed call log will be created for each participant in a locked excel file only accessible by study staff. This call log will detail each call made to participants, what number was called, what day/time, and what was said or if the study staff left a message (and which message). If study staff call the additional points of contact, that will be noted in the call log. The conversation between study staff and the additional contact will be summarized in case follow-up needs to occur. Study staff will attempt to contact participants who were unreachable throughout the duration of the study. Participants will be considered lost to follow up if they cannot be scheduled for their final dental assessment, i.e., within two months of their last scheduled study visit (Visit 6 or 7 depending upon initial enrollment). We will not replace any lost or withdrawn participants.

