8 STUDY PROCEDURES/EVALUATIONS

8.1 Study Procedures/Evaluations

All children in the study will have an oral assessment at ages 12 and 24 months with approximately half of children followed until 30-36 months with a third oral assessment. Oral assessments will include dmfs evaluation. Procedures for the oral assessments will be defined by the Caries Outcome Work Group of the ECC consortium. The criteria for the determination of dmfs measures will be according to Drury, et al.¹³ These criteria include the counting of cavitated caries lesions. Dmft scores for the secondary outcome will be derived from dmfs scores. The number of teeth with decayed surfaces will be divided by the number of erupted teeth to create the dmft score. If no teeth have been filled or are missing due to disease this will be dt rather than dmft.

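### The imputation model for missing final dmfs omits cohort or child age and the Visit 6 score, which biases the effect estimate if late dropout follows caries

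*Combined protocol and SAP*

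**What the plan says.** The imputation is described in two places that do not refer to each other. Section 12.4 imputes missing final dmfs within each arm "based upon key sociodemographic factors (maternal age and education; tribe; child sex) assuming the data are missing at random". Section 12.1 says the analysts "will incorporate 12 month assessments in models to multiply impute missing dmfs scores for the last assessment". Read together, the predictors are the 12-month score and these sociodemographic factors.

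The analysis model is wider: "We will include child sex, child age in months at follow up and site (Hopi/Crow) as covariates". The stated reason is that "age and sex are strongly associated with dmfs scores". No imputation method is named; section 12.4 says only "The primary outcome is a continuous variable".

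On the data available, section 8.1 states "All children in the study will have an oral assessment at ages 12 and 24 months". The early cohort, about half the sample, is examined once more at 30-36 months. Section 3.1 places the primary outcome at 24 months for the late cohort and at 30-36 months for the early cohort. Section 5.3 adds: "Participants will be considered lost to follow up if they cannot be scheduled for their final dental assessment", where the final assessment is Visit 6 or Visit 7 according to enrolment. Section 5.5.2 seeks a dmfs score at an early-termination visit and keeps data collected before a withdrawal. Neither 12.1 nor 12.4 gives such a score a role.

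**The concern.** Two useful predictors are left out.

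- **Cohort or child age.** Final exams take place at two different ages, and the plan's own figures show dmfs rising steeply between them. An imputation without age pools the two ages, while the analysis model then adjusts for age.
- **Visit 6 dmfs.** An early-cohort child who misses Visit 7 will normally have been examined at 24 months. That is the most recent caries measure, and the stated model has no place for it.

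Missing at random is credible only if whatever drives dropout is in the imputation model. If families leave after Visit 6 partly because of the caries found there, and the two arms differ in this or in caries level, the treatment effect is mis-estimated. With planned power of only 0.71, avoidable bias toward zero matters.

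The silence on method adds to this. A planned mean of 14 with SD 17.25 for a score that cannot be negative implies strong skew, which ordinary straight-line imputation handles poorly.

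**Working it through.** **1. The plan's own figure.** Section 12.2 gives 14 v 8.8, SD 17.25 and 141 per group. A 37% reduction is 0.37 × 14 = 5.18. SE = 17.25 × √(2/141) = 2.05. Power ≈ Φ(5.18/2.05 − 1.96) = Φ(0.56) = 0.71, as stated.

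**2. Size of the age gap.** Linear interpolation to 33 months gives 10.05 + 0.75 × (18.2 − 10.05) = 16.2, against 10.05 at 24 months. With half the children in each cohort, a pooled centre is (10.05 + 16.2)/2 = 13.1. Before other predictors, that is about 3 too high for the late cohort and 3 too low for the early cohort. These errors largely offset when losses are balanced across cohorts, so cohort alone moves the treatment effect little.

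**3. Number of children Visit 6 can help.** Planned loss is 0.19 × 350 = 66.5. The early cohort is about 175 (half) to 350 × 8/14 = 200 (section 4, recruits through month 8). If 2 to 7 attrition points fall after Visit 6 (assumed), the number is 0.02 × 350 = 7 to 0.07 × 350 = 24.5.

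**4. Simulations at n=350.** Taken from the documents: 1:1 allocation, 19% missing, age-2 and age-3 means and SDs, 37% reduction. Imputation was within arm. Bias = mean estimate − true effect; RMSE² = bias² + variance. The documents give no between-visit correlations, dropout slopes or dropout timing, so these are assumed:

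- **A:** gamma-type scores; 12-month mean 1.5; correlations 0.45 (12-24 months) and 0.84 (Visits 6-7); losses of 5/7/7 points before 12 months, from then to Visit 6, and after Visit 6; slope 0.6 log-odds per SD of last dmfs; true effect −4.85. Predictive mean matching before and after.
- **B:** negative binomial scores; latent correlations 0.5/0.8/0.4; slope on log(1 + latest dmfs), 0.8 unless stated; about a quarter of missing children have Visit 6 data in the main cases; true effect −5.28. Straight-line imputation before, matching after.
- **C:** correlations 0.5/0.8; losses 5/7/7; control-arm slope 0.6. Straight-line before, matching after.

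Before = 12.1 plus 12.4. After = Visit 6 dmfs and cohort added. Bias is toward zero unless marked.

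| Case | Bias before → after | RMSE before → after |
|---|---|---|
| A, control arm only | 1.04 → 0.56 (−46%) | 2.09 → 1.85 (−11%) |
| A, both arms | 15% → 8% too small | 1.74 → 1.73 |
| A, oral health arm only | 7% → 4% too large | 1.78 → 1.75 |
| A, random dropout | 1% too small → 1% too large | 1.81 → 1.81 |
| B, control arm only | 0.91 → 0.35 (−62%) | 2.02 → 1.77 (−12%) |
| B, control arm, slope 0.4 | 0.46 → 0.14 (−70%) | – |
| B, both arms | 0.50 → 0.19 (−62%) | 1.88 → 1.76 (−6%) |
| B, loss mostly after Visit 6 | 1.92 → 0.72 (−62.5%) | 2.58 → 1.99 (−23%) |
| B, loss almost all before Visit 6 | 0.11 → 0.16 | – |
| B, random dropout | 0.09 → 0.04 | – |
| C, control arm only | 0.66 → 0.48 (−27%) | 1.85 → 1.76 (−5%) |

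RMSE moves little because sampling variance dominates. In A, control arm only, 2.09² = 4.37, of which bias² is 1.04² = 1.08. Afterwards 1.85² = 3.42, of which bias² is 0.56² = 0.31.

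**5. What drives the gain (B, control arm only).** Bias is 1.59 with the 12.4 list alone, 0.91 with 12-month dmfs added, 1.02 with the same predictors and matching, 0.78 with cohort also added (straight-line), −0.09 with Visit 6 also added (straight-line), and 0.35 with Visit 6, cohort and matching. Visit 6 does most of the work on bias. Matching mainly lowers variance (RMSE 1.77 v 1.85).

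**6. Straight-line imputation with Visit 6.** It is accurate in B but overshoots in C (−0.61). In A's large-sample runs it overshoots by up to 12% and is closer than the plan in only 93 of 180 scenarios; at n=350 with control-arm dropout it raises RMSE from 1.84 to 2.01.

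**The case against.** The strongest reply is that the Visit 6 score may not be lost at all. Section 12.1 defines the outcome by the last exam, section 5.5.2 keeps data gathered before withdrawal, and 12.4 uses age as a covariate to handle unequal follow-up. Section 5.3 defines loss to follow-up but does not say how an available Visit 6 score is analysed. If Visit 6 stands in as the outcome, B leaves a bias of only about 0.2. This stands as an ambiguity: a reader might infer that the plan discards Visit 6, but the documents do not settle it. Sections 3.1 and 5.3 favour treating a missed Visit 7 as missing. Substitution is not free either: in A it gave an effect about 3% too small even under random dropout, and 8% too small to 9% too large otherwise.

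The reach is also small. Visit 6 cannot help the late cohort, whose Visit 6 is the outcome, or children lost earlier. That stands.

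Finally, A's before case uses matching, which the plan does not name, and assumptions favourable to the change. With straight-line imputation before, A's control-arm RMSE is 1.84, against 1.85 for matching with Visit 6: no gain. That also stands, and it is why the RMSE range starts at about zero.

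**Conclusion.** The omission is real and should be fixed, with medium confidence in its size. Cohort or child age and Visit 6 dmfs are absent from the stated imputation predictors, although age is in the analysis model and Visit 6 is scheduled for every child. If dropout after Visit 6 depends on Visit 6 caries, the estimate is biased. The bias is usually toward zero, but away from it when only oral health arm dropout follows caries. Across the assumed scenarios with caries-related loss after Visit 6, the change removes 27% to 70% of the bias at trial size, roughly a quarter to two-thirds. RMSE falls by about 0 to 23%. There is no material bias under random dropout, and little or no gain if loss occurs before Visit 6.

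Three stronger readings are not supported:

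- **That the change halves the total error.** Only bias falls by about that much, and only under some assumptions.
- **That the plan ignores earlier caries.** Section 12.1 brings in the 12-month score, which already removes much of the bias.
- **That a count-suited method is itself the remedy.** Matching without Visit 6 brought no gain in bias; the case for naming a method is that straight-line imputation with Visit 6 overshoots under some assumptions.

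**What to change.** State one imputation model, in the same words, in 12.1 and 12.4:

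- Impute within arm and in visit order, from site, child sex, maternal age and education, cohort (or scheduled age at the target exam), 12-month dmfs, Visit 6 dmfs for the early cohort, and any early-termination dmfs with its exam age. Scheduled age also supplies the analysis covariate for a child who was never examined.
- Name a method suited to a skewed, non-negative count, for example predictive mean matching with raw and log(1 + dmfs) predictors.
- Before unblinding, state whether a missed Visit 7 is imputed from Visit 6 (the reading 3.1 and 5.3 favour) or replaced by Visit 6 with age as covariate (a reading 5.5.2 and 12.1 allow).

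The cost is SAP wording and some programming, with no new data collection. Matching intervals run slightly short at this sample size: coverage in A was 0.90-0.94 with Visit 6 and 0.87-0.94 without.
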